4.7 Data Quality

Monitoring and auditing procedures defined/agreed by the sponsor will be followed, in order to comply with Good Clinical Practice (GCP) guidelines. Our center will be monitored at quarterly to ensure compliance with the study protocol, GCP and legal aspects. This will include on-site checking of the case report forms (CRF) for completeness and clarity, cross checking with source documents, and clarification of administrative matters.

4.8 Documentation

Entries made in the CRF must be either verifiable against source documents, or have been directly entered into the CRF, in which case the entry in the CRF will be considered as the source data. The source data parameter to be verified and the identification of the source document must be documented. The study file and all source data should be retained until notification given by the sponsor for destruction.

5 Ethical And Legal Aspects**5.1 Ethics Committee (EC) Or Institutional Review Board (IRB)**

Documented approval from appropriate IRBs will be obtained prior to study start, according to GCP, local laws, regulations and organizations. When necessary, an extension, amendment or renewal of the IRB approval must be obtained and retained in site files. IRB must supply to the sponsor, upon request, a list of the IRB Committee members involved in the vote and a statement to confirm that the IRB Committee is organized and operates according to GCP and applicable laws and regulations.

5.2 Ethical Conduct Of The Study

The procedures set out in this protocol, pertaining to the conduct, evaluation, and documentation of this study, are designed to ensure that the sponsor and investigator abide by *GCP Guidelines* and under the guiding principals detailed in the 1989 version of the *Declaration of Helsinki*. The study will also be carried out in keeping with applicable local law(s) and regulation(s). This may include an inspection by the sponsor representatives and/or Regulatory Authority representatives at any time. The investigator agrees to the inspection of study-related records by the Regulatory Authority/sponsor representatives, and must allow direct access to source documents to the Regulatory Authority/sponsor representatives.

Modifications to the study protocol will not be implemented by either the sponsor or the investigator without agreement by both parties. However, the investigator may implement a deviation form, or a change of, the protocol to eliminate an immediate hazard(s) to the trial subjects without prior IRB/Sponsor approval/favorable opinion. As soon as possible, the implemented deviation or change, the reasons for it and if appropriate the proposed protocol amendment should be submitted to the IRB/Sponsor. Any deviations from the protocol must be fully explained and documented by the investigator.

5.3 Regulatory Authority Approvals/Authorizations

Regulatory Authority approvals/authorizations/ notifications, where required, must be in place and fully documented prior to study start.

5.4 Subject Information And Consent

The Informed Consent Form (ICF) will be provided. Prior to the beginning of the study, the investigator must have the IRB written approval/favorable opinion of the written Informed Consent Form and any other written information to be provided to subjects. The written approval of the IRB together with the approved subject information/ICF must be filed in the study files.

Written informed consent must be obtained before any study specific procedure takes place. Participation in the study and date of informed consent given by the subject should be documented appropriately in the subject's files.

Discussion of the study with the patient will occur in person or via phone. While patients may be approached soon after their visit and/or admission begins, they can take time to consider and discuss participation with others before deciding. All questions will be answered by an investigator prior to signing the consent form. In rush/emergency transplant cases, the study will not be offered. If the patient wishes to enroll in the study, consenting will occur in person with a paper ICF or via phone conversation using DocuSign. The process followed will be fully documented with a consent progress note.

5.5 Confidentiality

All records identifying the subject will be kept confidential and, to the extent permitted by the applicable laws and/or regulations, will not be made publicly available.

Subject names will not be supplied to the sponsor. Only the subject number and subject initials will be recorded in the case report form, and if the subject name appears on any other document (e.g., pathologist report), it must be obliterated before a copy of the document is supplied to the sponsor. Study findings stored on a computer will be stored in accordance with local data protection laws. The subjects will be informed in writing that representatives of the sponsor, EC/IRB, or Regulatory Authorities may inspect their medical records to verify the information collected, and that all personal information made available for inspection will be handled in strictest confidence and in accordance with local data protection laws.

If the results of the study are published, the subject's identity will remain confidential.

The investigator will maintain a list to enable subjects' records to be identified.

6 Statistical Methods And Determination Of Sample Size

6.1 Statistical And Analytical Plans

6.2 Determination of Sample Size

Since this pilot study will be looking at feasibility and safety of a novel method of administration of C1INH, sample size determination was not performed.

7 Adverse Events (AEs)

7.1 Adverse Event (AE) Monitoring

7.2 Adverse Event (AE) Definitions

7.2.1 Adverse Events (AEs)

An AE is any untoward medical occurrence in a subject or clinical investigation subject administered with a pharmaceutical product. The AE does not necessarily have to have a causal relationship with this treatment. An AE can therefore be any unfavorable and unintended sign (including an abnormal laboratory finding), symptom, or disease temporally associated with the use of an investigational product, whether or not considered related to the medicinal product.

Adverse events associated with the use of a drug in humans, whether or not considered drug related, include the following:

- An AE occurring in the course of the use of a drug product in professional practice,
- An AE occurring from an overdose whether accidental or intentional,
- An AE occurring from drug abuse,
- An AE occurring from drug withdrawal.

- An AE where there is a reasonable possibility that the event occurred purely as a result of the subjects participation in the study (e.g. adverse event or serious adverse event due to discontinuation of anti-hypertensive drugs during wash-out phase) must also be reported as an adverse event even if it is not related to the investigational product.

The clinical manifestation of any failure of expected pharmacological action is not recorded as an AE if it is already reflected as a data point captured in the CRF. If, however, the event fulfills any of the criteria for a "serious" AE (SAE), it must be recorded and reported as such.

7.2.2 Serious Adverse Event (SAE)

An SAE is any untoward medical occurrence that at any dose:

- results in death
- is life-threatening
- requires in-patient hospitalization or prolongation of existing hospitalization
- results in persistent or significant disability or incapacity
- is a congenital anomaly or birth defect
- is an important medical event

Life-threatening: The term "life-threatening" in the definition of "serious" refers to an adverse event in which the subject was at risk of death at the time of the event. It does not refer to an adverse event which hypothetically might have caused death if it were more severe.

Hospitalization: Any AE leading to hospitalization or prolongation of hospitalization will be considered as Serious, UNLESS at least one of the following exceptions are met:

- The admission is pre-planned (i.e., elective or scheduled surgery arranged prior to the start of the study)

OR

- The admission is not associated with an adverse event (e.g., social hospitalization for purposes of respite care)

However, it should be noted that invasive treatment during any hospitalization may fulfill the criterion of 'medically important' and as such may be reportable as an SAE dependent on clinical judgment. In addition, where local regulatory authorities specifically require a more stringent definition, the local regulation takes precedent.

Disability: a substantial disruption of a person's ability to conduct normal life's functions.

Important medical event: Any adverse event may be considered serious because it may jeopardize the subject and may require intervention to prevent another serious condition. As guidance for determination of important medical events refer to the "*WHO Adverse Reaction Terminology - Critical Terms List*". These terms either refer to or might be indicative of a serious disease state.

Such reported events warrant special attention because of their possible association with a serious disease state and may lead to more decisive action than reports on other terms.

SAE medwatch reports **WILL NOT** be filled out for any prolonged hospital admissions or readmissions that are related to expected complications of the patients' primary disease (ESRD). For example, prolonged admissions for dialysis or readmission for fluid overload as a consequence of ESRD since this is an expected complication of the patients' disease state and not related to study drug. These events will be adjudicated by the PI. Otherwise, all SAEs medwatch reports will be submitted to the IRB, and FDA.

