4.6.2.5 Therapy Stopping Points

As indicated previously, the study will be halted and re-evaluated by the DSMB if any patient in the study group develops thrombosis of the allograft, thromboembolic events (TE) or evidence of coagulation abnormalities that would suggest impending TE. In addition, the study will be halted or stopped if any other known or unexpected AEs attributable to C1-inhibitor occur. Reassessment of the study goals and complications will be done and discussed with the DSMB prior to proceeding. A summary report will be submitted to the IRB and FDA.

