4.6.2.6 Primary Safety Endpoints

- Overall incidence of adverse events and serious adverse events and relationship to the study treatment including but not limited to, occurrence of infections, thrombosis of the allograft, vascular thromboses, bleeding, death, vital signs, and abnormal lab values.

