7.3 Reporting of Serious Adverse Events (SAEs) or Pregnancy

Serious adverse events (SAEs), including laboratory test abnormalities fulfilling the definition of serious, after signing the informed consent and during follow-up period must immediately (within 24 hours of the investigator's awareness) be reported to the person detailed in the study file. A *Serious Adverse Event Form* must also be completed within 24 hours of the investigator awareness and forwarded to the designated person as detailed in the study file. Each SAE must be followed up until resolution or stabilization by submission of updated reports to the designated person.

When required, and according to local law and regulations, SAEs must be reported to the IRB and Regulatory Authorities.

All AEs, SAEs, and SUSARs believed or possibly attributable to the investigational product must be reported to the IRB and FDA in accordance

CONFIDENTIAL C1INH (Berinert®) IRI Study in Kidney Transplant with the signed Pharmacovigilance Agreement, which will also be included in the study file and regulatory binder.

Pregnancy occurring during a clinical investigation, although not considered an SAE, must be reported to the IRB within the same timelines as an SAE on a *Pregnancy Monitoring Form*. The outcome of a pregnancy should be followed up carefully and any abnormal outcome of the mother or the child should be reported. This also applies to pregnancies following the administration of the investigational product to the father prior to sexual intercourse.

8 References

1. United States Renal Data System: 2015 USRDS Annual Data Report: Epidemiology of Kidney Disease in the United States, Bethesda, MD, National Institutes of Health, National Institute of Diabetes and Digestive and Kidney Diseases, 2015
3. WuK, FamureO, LiY, KimSJ: Delayed graft function and the risk of acute rejection in the modern era of kidney transplantation. *Kidney Int* 88: 851-858, 2015

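### Section 7.2.2 presumes that dialysis and fluid-overload admissions are unrelated to the study drug, which pre-fills the relatedness part of the primary safety endpoint

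*Combined protocol and SAP*

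**What the plan says.** Section 7.2.2 says of the MedWatch forms that none is to "be filled out for any prolonged hospital admissions or readmissions that are related to expected complications of the patients' primary disease (ESRD"). Its example is "prolonged admissions for dialysis or readmission for fluid overload as a consequence of ESRD since this is an expected complication", and it describes these events as an "expected complication of the patients' disease state and not related to study drug". It then adds: "These events will be adjudicated by the PI". All other SAE MedWatch reports go to the IRB and FDA.

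The places that depend on relatedness, or on these events being counted, are:

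- **4.6.2.6, primary safety endpoint:** "Overall incidence of adverse events and serious adverse events and relationship to the study treatment".
- **4.6.2.5, halting rule:** there are two limbs. Allograft thrombosis, thromboembolic events and coagulation abnormalities pointing to one trigger a halt with no attribution needed. Beyond those, "the study will be halted or stopped if any other known or unexpected AEs attributable to C1-inhibitor occur".
- **7.2.1:** failure of the expected drug action "is not recorded as an AE if it is already reflected as a data point captured in the CRF", but the next sentence restores recording and reporting whenever the event is serious.
- **7.2.4:** relatedness is a clinical decision on all the information available, weighing timing, underlying disease and pharmacology.
- **7.2.6:** every AE after consent goes into the case report form, with its relationship to the product.
- **7.3:** SAEs must within 24 hours "be reported to the person detailed in the study file", with an SAE form. Events believed or possibly attributable to the product go to the IRB and FDA.

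**The concern.** After a transplant, a prolonged stay for dialysis reflects how the graft is working, not simply the renal failure that preceded it. The product is infused into that graft by a route which Section 4.5.8 says is unapproved and may carry unforeseen risks. Worse graft function is therefore a plausible harm, and safety is the trial's primary objective (2.1). A rule that answers the causality question for this class before any event occurs works against that objective.

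At stake is whether an excess of such admissions in the C1INH arm could appear where the plan looks for drug-related harm: the relatedness tabulation, the attribution limb of the halting rule, and reporting of possibly attributable events.

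**Working it through.** The plan has no figure to reproduce: Section 6.2 says that no sample size was calculated, and no rate is given for these admissions. The check is a comparison of sections, followed by simple arithmetic on size.

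**1. Is the causality answer preset?** Section 7.2.2 labels the class unrelated. Section 7.2.4 requires a decision on each event from all available information. Both cannot govern the same admission. The label also sits badly with the hypothesis (2.0, and the 30–50% predicted reduction in 4.5.7) that the infusion changes delayed graft function, which Section 1.0 defines as dialysis in the first week.

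**2. Are the events still recorded?** Yes, on a fair reading. The waiver names only MedWatch reports. The hospitalisation rule in 7.2.2 treats a stay prolonged by an AE as serious and lists no exception for renal disease. Sections 7.2.1, 7.2.6 and 7.3 all require a serious event to be recorded. But 7.2.2 does not itself say that recording continues.

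**3. Where else would an excess show?** Need for dialysis and sessions per patient are primary efficacy endpoints (4.6.1.1), but only to day 30 and excluding dialysis for hyperkalemia. The synopsis lists first-month haemodialysis under safety; 4.6.2.6 and 4.6.2.7 do not. Fluid-overload readmissions are in no named endpoint. Section 3 provides for DSMB review of safety data and quarterly assessment of AEs and SAEs, but does not say that the DSMB sees dialysis by arm.

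**4. Size of the class.** Inputs: 20 patients per arm and 40–50% expected delayed graft function (4.5.1). Delayed graft function stands in for the class and is an upper bound, since not every dialysed patient has a prolonged or repeat admission.

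- Placebo arm: 20 × 0.40 = 8 to 20 × 0.50 = 10.
- C1INH arm with no effect: also 8 to 10, so 16 to 20 of 40 in all.
- C1INH arm with the predicted reduction: 20 × 0.40 × 0.50 = 4 to 20 × 0.50 × 0.70 = 7.

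**5. Effect on the relatedness comparison.** Let r be the chance that a blinded assessor calls such an event related, the same in both arms. The expected difference in related events is r × 20 × (p_C1INH − p_placebo). For an assumed excess of 12/20 against 8/20 this is 4r, between 0 and 4 events. The presumption sets r = 0, so the contribution is 0 whatever the true excess.

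**6. Why recording should be stated outright.** Assume a background rate q of other SAEs, independent of these admissions. A 20-point excess of admissions adds (1 − q) × 0.20 to the difference in any-SAE incidence: 0.18 at q = 0.10 and 0.12 at q = 0.40. If someone took the waiver to mean that these events are not SAEs, it would add 0.

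**7. Strength of the remaining arm comparison.** With n = 20 per arm and two-sided α = 0.05 (assumed; the plan states none), power = Φ{[|p₁ − p₂|√n − 1.96√(2p̄(1 − p̄))] / √[p₁(1 − p₁) + p₂(1 − p₂)]}. For 0.40 against 0.60: (0.894 − 1.386)/0.693 = −0.71, so power is 24%. For 0.50 against 0.70 it is 25%. Exact Fisher power is 14% and 16%.

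**8. The opposite extreme.** If every such event counted as attributable, the chance of at least one among 20 C1INH patients would be 1 − (1 − p)²⁰: 1 − 0.80²⁰ = 98.9% at p = 0.20, and above 99.9% at p = 0.50. Blanket attribution would be as uninformative as blanket non-attribution.

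**The case against.** The strongest reply is that the waiver is narrow and the trial has other ways to see the harm.

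- **Recording stands.** Only MedWatch submissions are waived. A reader might infer that these admissions vanish from the primary safety comparison; the recording rules in 7.2.1, 7.2.2, 7.2.6 and 7.3 do not support that. Nor does the first half of 7.2.1 excuse them, because its serious-event exception applies. The 24-hour report in 7.3 goes to a designated person, a different route from MedWatch, so the two can coexist.
- **Much of the halting rule stands.** A reader might infer that graft loss through thrombosis would escape it. It would not: that limb needs no attribution. Only the attribution limb is affected.
- **Causality is not wholly closed.** The waiver is conditional on the stay being a consequence of renal disease, and the principal investigator, who is blinded (4.5.3), adjudicates. That leaves some room, but no criteria are given and the sentence before has already stated the answer. Blinding means that the label falls alike on both arms; it does not restore a difference that the label suppresses.
- **Dialysis is compared by arm, along with eGFR and graft survival.** This is the best part of the reply. With delayed graft function so common, one admission says little about cause, and an excess shows better in counts by arm. But the dialysis comparison stops at day 30, omits dialysis for hyperkalemia, leaves out fluid-overload readmissions, and is not stated to reach the DSMB during the trial.
- **Harm is not shown to be likely.** This is correct. The documents predict benefit and give no harm rate; plausible is as far as they go.

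**Conclusion.** The point holds in a limited form and should be acted on. Section 7.2.2 presumes the cause of a class of serious events that the trial's own hypothesis says the drug may influence, contrary to 7.2.4. The consequences are a biased relationship component in the primary safety endpoint and, on a literal reading, no route for these events into the attribution limb of 4.6.2.5 or the possibly-attributable reporting in 7.3. Overall AE and SAE incidence and the thrombosis limb of the halting rule are not affected.

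Up to 16–20 of 40 patients could fall in the class, on the assumption that delayed graft function bounds it from above. The true number may be much smaller. The 12/20 against 8/20 excess, the background SAE rates and the power figures are illustrations on assumed values, not findings about this product.

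**What to change.** 1. In 7.2.2, strike the closing clause that declares these admissions unrelated to the study drug.
2. State that the waiver covers individual MedWatch submissions only, and that these events are still recorded as SAEs, with relatedness judged event by event under blinding according to 7.2.4.
3. Tabulate prolonged dialysis admissions and fluid-overload readmissions by arm in the safety report, and include the counts by arm in the quarterly review for the DSMB.
4. Reconcile 7.2.2 with 7.2.1, 7.2.4, 7.2.6, 7.3 and 4.6.2.5, so that each says the same about recording, relatedness and reporting of these events. No new halting rule is proposed here.

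The cost is wording and some extra SAE forms for patients already in follow-up. Appendix A already schedules dialysis and adverse event assessments through day 180, so no new visits are needed.

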7.2.3 Unexpected Adverse Event (AE)

An unexpected AE is any adverse drug event, the specificity or severity of which is not consistent with the current Investigator Brochure (or Package Insert for marketed products). Also, reports which add significant information on specificity or severity of a known, already documented adverse event constitute unexpected AEs. For example, an event more specific or more severe than described in the Investigator Brochure would be considered "unexpected". Specific examples would be; (a) acute renal failure as a labeled adverse event with a subsequent new report of interstitial nephritis and (b) hepatitis with a first report of fulminant hepatitis.

7.2.4 Relationship Of Adverse Event To Investigational Product

The assessment of the relationship of an AE to the administration of study drug is a clinical decision based on all available information at the time of the completion of the case report form.

An assessment of 'No' would include:

1. The existence of a clear alternative explanation, e.g., mechanical bleeding at surgical site; or
2. Non-plausibility, e.g., the subject is struck by an automobile when there is no indication that the drug caused disorientation that may have caused the event; cancer developing a few days after the first drug administration.

An assessment of 'Yes' indicates that there is a reasonable suspicion that the adverse event is associated with the use of the investigational drug.

Factors to be considered in assessing the relationship of the adverse event to study drug include:

- The temporal sequence from drug administration: The event should occur after the drug is given. The length of time from drug exposure to event should be evaluated in the clinical context of the event
- Recovery on discontinuation (de-challenge), recurrence on reintroduction (re-challenge): Subject's response after drug discontinuation (de-challenge) or subject's response after drug re-introduction (re-challenge) should be considered in the view of the usual clinical course of the event in question

- Underlying, concomitant, intercurrent diseases: Each report should be evaluated in the context of the natural history and course of the disease being treated and any other disease the subject may have
- Concomitant medication or treatment: The other drugs the subject is taking or the treatment the subject receives should be examined to determine whether any of them may be suspected to cause the event in question
- The pharmacology and pharmacokinetics of the test drug: The pharmacokinetic properties (absorption, distribution, metabolism and excretion) of the test drug(s), coupled with the individual subject's pharmacodynamics should be considered.

